2. Received the last lethally irradiated GM-CSF transfected allogeneic pancreatic cell lines Panc 10.05 and Panc 6.03 as a participant in either one of the Hopkins IRB protocols: application number 96-01-25-01 entitled “A Phase I Clinical Trial of Lethally Irradiated Allogeneic Pancreatic Tumor Cells Transfected with the GM-CSF Gene for the Treatment of Adenocarcinoma of the Pancreas”, SKCCC J9617, or application number 00-01-13-02, entitled “A Safety and Efficacy Trial of Lethally Irradiated Allogeneic Pancreatic Tumor Cells Transfected with the GM-CSF Gene in Combination with Adjuvant Chemoradiotherapy for the Treatment of Adenocarcinoma of the Pancreas”, SKCCC J9988, at least 6 months ago;

OR

Completed surgery and any adjuvant therapy at least 28 days prior. Treatment administered in conjunction with surgery is at the discretion of the local oncologists. Options may include: neo-adjuvant chemotherapy, neo-adjuvant radiation, post-surgical adjuvant chemotherapy, post-surgical adjuvant radiation.

3. Received the last anti-cancer therapy at least 28 days ago.
4. Provide informed consent.
5. Have an Eastern Cooperative Oncology Group (ECOG) performance status of 0 or 1.
6. Have adequate hematologic function (Hemoglobin \geq 9 gm/dl, ANC \geq 1500#/cu mm, platelets \geq 100,000 K/cu mm)
7. Have adequate renal function (Serum creatinine \leq 2 mg/dL).
8. Have adequate hepatic function (Bilirubin \leq 2.0 mg/dL, unless known Gilbert's Syndrome; AST, ALT and amylase \leq 2x upper limit of normal; Alk Phos \leq 5x upper limit of normal.)
9. Agree to use adequate birth control, if of childbearing potential.

3.2.3 Exclusion Criteria for First Vaccination:

Research participants with any of the following will be excluded from study entry:

1. Radiographical evidence of pancreatic cancer disease recurrence.
2. Documented history of autoimmune diseases including systemic lupus erythematosus, sarcoidosis, rheumatoid arthritis, glomerulonephritis, or vasculitis.
3. Uncontrolled medical problems.
4. Systemic steroid therapy within 28 days before vaccine administration.
5. Anticipated need for systemic steroid therapy within 28 days after vaccine administration.
6. Evidence of active infections.
7. Pregnant.
8. History of another cancer (other than pancreatic cancer) in the past five years except for treated non-melanoma skin cancer, superficial bladder cancer, or carcinoma-in-situ of the cervix.

3.2.4 Inclusion Criteria for Boost Vaccination:

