4.0 Statistical Considerations

4.1 Sample Size

The primary statistical endpoint of this study is to evaluate the safety and feasibility of vaccine boosting with lethally irradiated allogeneic pancreatic tumor cells transfected with the GM-CSF gene. Among patients who have previously been treated with the vaccine, the cohort is limited to those who continue to have no disease recurrence for at least 1 year after treatment. Currently, there are three potentially eligible patients from the original phase I study, and 14 from the phase II study. A total of up to 17 previously treated patients will be eligible to continue to receive vaccine treatment in the form of semi-annual boosts. The second cohort of vaccine naïve patients who have been recurrence free for at least 28 days following adjuvant therapy will be given three priming vaccines each a month apart, followed by semi-annual vaccine boosts in order to determine the feasibility of administering the vaccination to vaccine naïve patients and to obtain initial estimates of the efficacy of such treatment with respect to prolonging disease-free status. As of Amendment #9, participants will be switched to annual vaccinations. We will base our determination of feasibility by estimating the proportion of patients with a dose limiting toxicity (DLT) within 28 days of the first vaccine treatment. Between 20 and 45 vaccine naïve patients will be included. An initial group of 20 patients will be recruited and an interim analysis will be performed in order to guard against excessive toxicities relating to treatment. No DLTs have been observed in either the phase I or II studies. If there is significant evidence that more than 10% of the vaccine naïve patients have dose limiting toxicities within 28 days of the first vaccination, then the trial will be halted. If 6 out of 20 of the initial patients have DLTs, the lower bound of the exact 95% confidence interval for the proportion of patients with a DLT is 11.89%. Therefore, we will halt the trial due to excessive toxicity at the interim analysis if 6 or more patients have a DLT within the first 28 days of their first vaccine. Otherwise, an additional 20 vaccine naïve patients will be accrued. If 20 patients are accrued, the maximum width of the 95% confidence interval estimate of the proportion of patients with a DLT is 0.438. If the full cohort of 40 patients is accrued, then the maximum width of the 95% confidence interval is 0.309.

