4.3 Analysis of Secondary Endpoints

The analysis of the remaining endpoints are primarily descriptive in nature and are intended to be used to generate estimates of efficacy and hypotheses to be tested in later trials. For each endpoint, separate analyses will be performed for the vaccine naïve and vaccine treated patients.

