4.3.1 Efficacy endpoints

The primary efficacy endpoint of interest is the overall survival (OS) of patients treated with vaccine boosts. The overall survival is defined as the time from the first vaccine boost until death. If a patient is lost to follow-up or the study is ended prior to death, the patient will be considered censored at their last recorded follow-up. For each cohort, Kaplan Meier curves will be constructed and the median survival estimates will be calculated with 95% confidence intervals using Greenwood's formula. Since the time between completion of treatment and the initiation of vaccine boosts will vary among subjects, we will use a Cox proportional hazards model to adjust for this delay in boosts.

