We are also interested in investigating the effect of vaccine boosts on recurrence free survival (PFS). Patients who are treated at Johns Hopkins will be followed every 3 months and evaluated for recurrence. However, the standard of care follow-up varies from institution to institution. In order to prevent biasing our results, it is necessary to coarsen the follow-up interval so that every individual is evaluated at the same time points regardless of the institution. For example, if the only visits held in common among all patients were the semi-annual exams prior to vaccine boosting, it would be necessary to only consider the status of the JH patients at those two time points regardless of recurrence information gained from the additional 2 visits. This coarsening of the data may cause an overestimation of PFS. In order to take into account both potential forms of bias, we will perform our analysis of PFS on the entire cohort as well as the subpopulation of patients from Johns Hopkins (estimated to be approximately 50% of the research participants). PFS will be defined as the time from the first vaccine until evidence of disease recurrence. If a patient withdraws from the study prior to being diagnosed with progressive disease, they will be censored at the date of their last follow-up visit. If an individual dies prior to being diagnosed with progressive disease, they will be considered to have progressed at the date of their last follow-up visit. This is a conservative estimate if we count the disease recurrence at the next planned visit then this will bias the PFS time upward. The PFS will be summarized using Kaplan-Meier curves and estimates of median PFS with 95% confidence intervals based upon Greenwood's formula. Due to potential causes of bias discussed earlier, the results will be considered extremely preliminary. If the PFS estimates for patients treated at Johns Hopkins appear to be lower than that of the population as a whole and the Johns Hopkins patients are followed at more frequent intervals than the other patients, then this indicate that an overestimation of PFS may exist. No formal comparison is planned due to the small sample size. Such results could affect the future planning of follow-up treatment for patients in subsequent trials.

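### OS from first boost and PFS from first vaccine depend on the mix of delays enrolled; the planned Cox model does not correct the reported curves, and PFS has no handling of delay

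*Combined protocol and SAP*

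**What the plan says.** In section 4.3.1, "The overall survival is defined as the time from the first vaccine boost until death". Kaplan-Meier curves and medians are planned for each cohort. The reason for the extra model is "Since the time between completion of treatment and the initiation of vaccine boosts will vary among subjects", and the remedy is "we will use a Cox proportional hazards model to adjust for this delay in boosts". No reference delay, functional form or adjusted estimate is named.

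For recurrence, "PFS will be defined as the time from the first vaccine until evidence of disease recurrence". The same section discusses bias from unequal visit schedules at length but does not mention delay.

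Section 4.3 adds that "separate analyses will be performed for the vaccine naïve and vaccine treated patients", and every patient is vaccinated, so the model contains no comparator.

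Entry depends on the outcome process. Sections 3.1, 3.2.3 and 3.2.5 bar radiographic recurrence at the first and every later vaccination. For previously vaccinated patients, section 4.1 says "the cohort is limited to those who continue to have no disease recurrence for at least 1 year after treatment". For vaccine-naïve patients, section 3.2.2 asks for "Completed surgery and any adjuvant therapy at least 28 days prior", which is a minimum with no maximum. Their OS clock starts later still, at the boost that follows the priming course.

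Section 5.1 compares results with historical controls matched on stage, surgery and adjuvant therapy.

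**The concern.** A patient vaccinated long after treatment has already shown that he or she did not recur early. If risk differs between patients, such a person has a better outlook on the day the clock starts than one vaccinated soon after treatment, whatever the vaccine does. The curves therefore mix patients selected to different degrees, and they shift with the delays that happen to be enrolled.

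The plan sees that delay matters, but the step it takes does not reach the figures it will report. Two misreadings could follow. The delay hazard ratio could be taken as evidence on when to boost, which is a design question for later trials. The from-vaccine and from-boost curves could also be set beside historical controls who were not required to be recurrence free for any comparable time.

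**Working it through.** The plan gives no effect size, event count or follow-up for this model, so it has no figure of its own to reproduce.

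**1. What the Cox model changes.** Its only named covariate is delay. With no treatment term there is no vaccine effect to free from confounding. A Kaplan-Meier curve and its median do not use the covariate, so they stay as they were. Adjusted survival could be predicted from the model at a chosen delay, but the plan does not ask for it.

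**2. Which way the delay coefficient leans.** OS from the boost was simulated with no effect of the vaccine or of its timing. Patients were kept only if recurrence free at the boost, and delay in years was the covariate. These inputs are assumptions: median time to recurrence about 1.5 years (1.2 in the non-cured), median death 0.75 years after recurrence, 5 years of follow-up, delays uniform over 1 to 6 years (previously vaccinated) or 0.75 to 2.5 years (naïve).

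| Recurrence hazard | HR per year, previously vaccinated | HR per year, naïve |
|---|---|---|
| Constant | 1.00 | 1.00 |
| Rising (Weibull 1.5) | 1.10 | 1.14 |
| Falling (Weibull 0.7) | 0.93 | 0.91 |
| Frailty, variance 0.5 | 0.90 | 0.87 |
| Frailty, variance 1 | 0.86 | 0.82 |
| 20% cured | 0.66 | 0.73 |

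A nominally significant protective result appeared in 0.6% to 13% of trials at n=17 and 0.9% to 11% at n=45. Under a constant hazard, the 95% range of the estimate was 0.57 to 1.66 (n=17) and 0.48 to 2.05 (n=45).

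**3. A steeper case.** Section 2.7.3 gives 6/14 disease free at one year and three patients still disease free. Read as a cured fraction c = 3/14, the rest recur at λ = −ln[(6/14 − 3/14)/(11/14)] = −ln(3/11) = 1.30 per year. With n=45, delays of 0.73 to 3 years and 4 years of follow-up, the median delay HR was about 0.35 per year, and 56% of trials were falsely protective. Capping delay at 1.5 years cut that to 11% to 14%. With 20% cured and a 1.2-year median in the rest, it was 10% to 13% (delays to 3 years) or 5% to 6% (to 2 years).

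**4. Which hazard shape is plausible.** A constant rate at the phase I one-year figure leaves (6/14)^5 = 0.0145 disease free at 5 years, or 14 × 0.0145 = 0.2 patients, against three seen. That points to mixed risk. The length of follow-up is not stated, however. The best-fitting constant rate is rejected at 5 years (p=0.014) but not at 3 (p=0.17).

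**5. Recurrence-free survival: two clocks.** Let S(t) = c + (1 − c)e^(−λt), with c and λ as in step 3. Assume first vaccination is uniform over a = 0.1 to b = 3 years after resection, among those still recurrence free.
- Time since resection, from year 0.1: S(1)/S(0.1) = 0.429/0.904 = **0.47**.
- From-vaccine clock at one year: ∫S(v+1)dv / ∫S(v)dv over a to b. The denominator is 0.2143 × 2.9 + (0.786/1.30)(e^(−0.13) − e^(−3.90)) = 0.621 + 0.519 = 1.140. The numerator is 0.621 + 0.519 × 3/11 = 0.763. The ratio is **0.67**.
- With b = 1.5: (0.300 + 0.445 × 3/11)/(0.300 + 0.445) = 0.421/0.745 = **0.57**.

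A large simulated sample analysed by Kaplan-Meier with delayed entry matched the generating curve within 0.01 at 0.5, 1, 2 and 3 years.

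**6. Does delayed entry also repair OS?** No. With OS on time since treatment and entry at the boost, the null delay HR was 0.69 to 0.79 (previously vaccinated) and 0.67 to 0.76 (naïve) for all six shapes, including the constant one. A patient who has just entered is known to be recurrence free. One who entered earlier may already have recurred.

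**The case against.** A reader might infer that a single-arm Cox model cannot adjust anything. That goes too far: it can give survival at a fixed or averaged delay, which is ordinary case-mix adjustment. The gap is that the plan does not name such an estimate.

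A reader might also infer that the delay coefficient is bound to show later boosting as protective, purely because late-boosted patients have already survived. The documents do not support this. The sign depends on the hazard shape, which they do not give. The OS clock starts at the boost, so waiting time is not credited as survival; this is selection on prognosis. A real timing effect could be present and could not be separated from it.

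The sizes are also open to challenge. The phase I patients were themselves vaccinated, at four dose levels, and their disease-free time ran from diagnosis. The exact 95% interval for 3/14 is 5% to 51%. The spread of delays is assumed throughout.

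Finally, section 4.3 calls these analyses "primarily descriptive in nature and are intended to be used to generate estimates of efficacy and hypotheses to be tested in later trials", section 4.3.1 treats the PFS results as very preliminary, and the halting rule rests on toxicity alone. It would be wrong to call the estimates uninterpretable. This lowers the severity. It does not remove the point, because the estimates are meant to inform later trials and section 5.1 sets results against controls.

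**Conclusion.** The concern holds in a limited form. Entry conditional on freedom from recurrence, with no upper limit on delay, makes both curves depend on the delays enrolled. The Cox model as written leaves the reported curves and medians uncorrected, and PFS is not adjusted for delay at all.

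If risk is heterogeneous, as the phase I long-term survivors suggest, the delay hazard ratio probably favours later boosting with no true timing effect. It is null under a constant hazard and can reverse under a rising one. The chance of a falsely protective result ran from under 1% to 56% across the assumptions tried, so no single figure should be quoted. The gap of 0.67 against 0.47 is likewise an illustration and shrinks with shorter delays.

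The firmest practical consequence is for section 5.1: the controls are not matched on recurrence-free time, so the from-vaccine curve would tend to look better than theirs if risk is heterogeneous. No primary conclusion or stopping decision is affected.

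**What to change.** 1. **Recurrence-free survival.** Add a Kaplan-Meier analysis on time since resection, with delayed entry (left truncation) at the first on-study vaccination, starting where at least 5 patients are at risk. Use this curve for any historical comparison, with the control curve started at the same time point among controls still recurrence free. State its assumption: among patients still event free, entry time is independent of prognosis.

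2. **OS.** Keep delay in the Cox model only to report survival at a stated reference delay, with the functional form fixed in advance. Say that the delay hazard ratio reflects selection and is not an effect of boost timing. Do not rely on delayed entry alone for OS, because entry requires freedom from recurrence and not just being alive.

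The cost is a few sentences in the analysis plan and a standard survival-software option. It needs dates of resection and end of treatment, and the plan already relies on the latter. The downsides are thin early risk sets, wide intervals in the cohort of 17, and probably a less favourable recurrence-free curve.

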Data and samples may be obtained from Day-28 to Day 0

1. A clinical evaluation to include vital signs, ECOG status, weight, review of systems, physical examination, and toxicity evaluation.

2. CT scans of the abdomen, pelvis, and chest. If the CT scan is not done at Hopkins, the research participant must provide the report and a copy of the scans. If the research participant is allergic to the CT scan contrast or is contraindicated, a non-contrast CT of the chest and a MRI of the abdomen and pelvis will be obtained.
3. A leukapheresis for in vitro studies will be encouraged. If the research participant refuses a leukapheresis, approximately 200 cc of blood will be drawn. As of Amendment #8, research bloods are no longer required to be collected.
4. Blood testing to include CBC/diff, absolute eosinophils, absolute neutrophils, absolute lymphocytes, comprehensive chemistry panel including electrolytes, albumin, BUN, creatinine, AST, ALT, total bilirubin, and alkaline phosphatase, amylase, and CA 19-9.
5. Research blood: 20 cc for serum banking. As of Amendment #8, research bloods are no longer required to be collected.
6. Pregnancy test for women of childbearing potential. Urine pregnancy test preferred.
7. If not previously enrolled on IRB # NA_00036444 (SKCCC J0248) entitled, Long term follow-up of patients who received lethally irradiated allogeneic pancreatic tumor cells transfected with the GM-CSF gene, the research participant will be encouraged to join the long-term follow-up study.

Day 0

1. Administration of vaccine (Topical lidocaine-based anesthetic may be placed about 1-2 hours prior to planned vaccine administration time to the intended vaccine sites.)
2. Vital signs before and after vaccine administration
3. Photograph of vaccine sites (if clinically indicated)
4. Assessment for toxicities
5. Monitor for 30 minutes after vaccine administration
6. Tetanus toxoid boost if last tetanus vaccination > 10 years. Tetanus/diphtheria (Td) may be substituted if tetanus alone is not available. If both are not available, no tetanus vaccine will be administered.

Day 28 after Boost Vaccine (-3/ + 14 days)

1. A leukapheresis for in vitro studies will be encouraged. If the research participant refuses a leukapheresis, approximately 200 cc of blood will be drawn. As of Amendment #8, research bloods are no longer required to be collected.
2. Assessment for toxicities and vaccine site reactions from previous vaccinations, and medications.

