If the research participant is unable to return to Johns Hopkins for the off-study visit, effort will be made to obtain medical records that may include laboratory and imaging tests results, pathology reports, and health care providers' notes. Data may also be obtained regarding toxicity and disease status by study clinician contact with the research participant, his/her family, or health care providers. The surveys may be mailed to the research participant's home with a stamped return envelope. Fax and electronic correspondence for the diaries and surveys is also acceptable. Arrangements may be made for the research samples to be obtained locally and shipped to the Hopkins' [name] Lab.

If the off-study visit is within 28 days of a protocol-specified visit in which the assessments and samples were obtained, the off-study assessments and specimens need not, but may be, repeated.

Research Samples

De-identified samples may be shared with other investigators with written authorization from the principal investigator. Additional samples may be collected for research purposes, including, but not limited to those obtained through biopsies, surgeries, and autopsies. As of Amendment #8, research bloods are no longer required to be collected.

Table 3. Study schema including toxicity and immune monitoring for Prime Vaccine #1 and each Boost Vaccination.

Assessment	Day 0 ¹	Day 1	Day 2	Day 3	Day 4				Day 28 ²
Clinical evaluation	X								
CT abd/chest/pelvis	X								
Vital signs ³	X	X ⁴		X ⁴					X ¹⁰
Toxicity assessment/evaluation ⁵	X	X ⁴		X ⁴					X ^{5,6}
Vax site assessment ⁵		X ⁴		X ^{4,6}					X ^{5,6}
Heme/ diff/abs.eos	X								
Chemistries ⁷	X								
CA 19-9	X								
Amylase	X								
Leukapheresis or PBL in vitro studies ⁸	X								X
Research blood: HLA typing and EBV testing ⁹	X								
Research blood: Serum banking ⁸	X								
Vaccine site biopsy ⁸	X ⁹								
Photograph, if indicated ⁹	X	X ⁶		X ⁶					X ⁶

¹ May be done up to 28 days prior to Day 0. Additional leukapheresis may be performed for an interesting immunological response.

² Day 28 (-3/ +14 days) assessments and samplings are to be done after each vaccination.

³ Vital signs include temperature, pulse rate, respiration rate, and blood pressure

⁴ At first vaccination only.

⁵ Assess to resolution.

⁶ Information may be obtained by phone, e-mail, fax, and/or through the evaluation by the local health care provider, if unable to assess in person.

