3.4.6 Off-study

Research participants will be discontinued from participating in this study for the following circumstances:

- ◆ There is radiographic evidence of pancreatic cancer recurrence.
- ◆ Serious vaccine related adverse events occur.
- ◆ The vaccine supply is exhausted.
- ◆ The research participant is noncompliant, is unable to comply with the treatment plan, or requests withdrawal.
- ◆ The research participant is receiving concomitant immunotherapy, chemotherapy, radiotherapy, or other biological or gene therapy.

If determined to be off-study, the research participant will be followed for 28 days after the administration of the last vaccine for toxicities related to the vaccine, or longer, if vaccine-related toxicities occur. Whenever possible, the research participant will be asked to have the tests indicated for the day 28 visit as the off-study visit, unless this was done within 28 days of the off-study date.

If the research participant consents there will be a lifelong follow-up through participation in [name] study, IRB # NA_00036444 (SKCCC J0248) entitled, Long term follow-up of patients who received lethally irradiated allogeneic pancreatic tumor cells transfected with the GM-CSF gene.

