5.0 Response Criteria

5.1 Evaluation of Clinical Activity

Most patients will have only minimal residual disease at the time of enrollment. Therefore, there will be no evaluable disease to measure at baseline. Patients will be monitored for disease-free and overall survival. The results from this trial will be compared to historical controls seen at the Johns Hopkins Hospital (5). Patients recently seen at the Johns Hopkins Hospital who can be matched for pathologic stage, surgical intervention, and adjuvant combination chemotherapy and radiation therapy, are the most accurate group of historical controls since our institution has the largest reported experience treating patients with this disease and has recently reported the best survival statistics for current interventions (5).

Patients may undergo standard of care evaluations consisting of abdominal, chest, and pelvis CT scans at regular intervals to evaluate for local recurrence and distant metastases. In addition, any patient presenting with symptoms will undergo evaluation for metastases. Recurrent disease is defined as evidence of either local or metastatic recurrence by CT scan.

The serum tumor marker CA19-9 lacks a sufficient sensitivity and specificity to serve as reliable indicators of response. The CA 19-9 levels will be followed to evaluate whether large and persistent changes might correlate with either in vitro immune responses or with time to clinical recurrence.

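### PFS censors withdrawals at the last follow-up visit rather than the last negative scan, which can bias PFS upward when that visit had no imaging and falls at or after a due scan

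*Combined protocol and SAP*

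**What the plan says.** Section 4.3.1 of the combined protocol and SAP states: "PFS will be defined as the time from the first vaccine until evidence of disease recurrence". For patients who withdraw "prior to being diagnosed with progressive disease, they will be censored at the date of their last follow-up visit". The term follow-up visit is not defined, and no sentence ties it to a scan.

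Section 5.1 states: "Recurrent disease is defined as evidence of either local or metastatic recurrence by CT scan". Section 3.4.1 allows MRI of the abdomen and pelvis, with non-contrast chest CT, when contrast cannot be given.

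Imaging is scheduled as follows:

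- **With a scan.** The Table 3 row "CT abd/chest/pelvis" is marked only at Day 0, for the first vaccination and each boost. The scan may be done up to 28 days earlier.
- **Without a scan.** The visit lists for primes 2 and 3, Day 28 after prime 3, and "Day 28 after Boost Vaccine (-3/ + 14 days") contain none.
- **Optional.** At extra visits (3.4.1), and while a boost is delayed for persistent vaccine reactions (3.4.1.4), imaging may be obtained but is not required.
- **Off-study.** The off-study list in 3.4.1 includes CT. Section 3.4.6 says that, whenever possible, "the research participant will be asked to have the tests indicated for the day 28 visit as the off-study visit", and the Day 28 list has no CT. For a patient who cannot return, 3.4.1 seeks records, which may include imaging, and also allows disease status through clinician contact.

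For the whole cohort, 4.3.1 says that "it is necessary to coarsen the follow-up interval so that every individual is evaluated at the same time points regardless of the institution". A second analysis is restricted to Johns Hopkins patients.

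**The concern.** Recurrence-free status is known only up to the last negative scan. If the censoring date is a later visit without imaging, the patient is credited with recurrence-free time that nobody assessed. This matters when the later date reaches a time point at which other patients' scans are read. The unscanned patient then enlarges the Kaplan-Meier denominator and cannot enter the numerator.

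The route that could produce this is a patient who declines a boost and has an off-study visit without CT around or after the date when the pre-boost scan was due. With yearly boosts the last scan could then be about 12 months old.

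Section 4.3.1 takes trouble over upward bias. It warns that coarsening may overstate PFS, and it dates deaths conservatively. It does not name the censoring date as a source. The estimates are meant to inform later trials (4.3), and section 5.1 plans a comparison with historical controls, where an upward error would flatter the vaccine.

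**Working it through.** The plan states no PFS sample size, event count or expected median, so there is no figure of its own to reproduce.

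**1. Do the scheduled visits without a scan reach the next scan?** After a boost, the last such visit is at 28 days, or 42 with the window. In the priming phase it is at 28 + 28 + 28 = 84 days, or 31 + 31 + 42 = 104 with the windows. If the scan was taken 28 days early, the gaps since the scan are 42 + 28 = 70 and 104 + 28 = 132 days. The first boost, six months after prime 3, comes at about 56 + 182 = 238 days (month 8). The scheduled visits therefore precede the next scan. On a common grid both censoring dates give the same curve.

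**2. A last visit without a scan at or after a due scan.** Let q be the share recurred by that scan among patients still at risk, and w the share of them who leave unscanned with a visit dated there. Withdrawal is taken as unrelated to recurrence. Events are q(1 − w) and the denominator is 1, so Kaplan-Meier gives 1 − q(1 − w) instead of 1 − q. The bias is q × w. Censoring at the last negative scan gives 1 − q(1 − w)/(1 − w) = 1 − q.

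Assumptions: constant hazard and common scans at months 8 and 20. The one-year recurrence-free rate is 43% (section 2.7.3, 6/14, measured from diagnosis, so only an anchor) or 75% (assumed). The documents give no w.

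Month 8: q = 1 − 0.43^(8/12) = 0.430, or 1 − 0.75^(8/12) = 0.175. From month 8 to 20: q = 0.57 or 0.25. The month 20 estimate is the product of the two factors.

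| One-year rate | w per scan | Month 8 (true) | Bias, points | Month 20 (true) | Bias, points |
|---|---|---|---|---|---|
| 43% | 1% | 0.574 (0.570) | 0.4 | 0.250 (0.245) | 0.5 |
| 43% | 2% | 0.578 | 0.9 | 0.255 | 1.0 |
| 43% | 10% | 0.613 | 4.3 | 0.298 | 5.3 |
| 43% | 20% | 0.656 | 8.6 | 0.357 | 11.2 |
| 75% | 1% | 0.827 (0.825) | 0.2 | 0.622 (0.619) | 0.3 |
| 75% | 2% | 0.829 | 0.3 | 0.626 | 0.7 |
| 75% | 10% | 0.843 | 1.7 | 0.653 | 3.4 |
| 75% | 20% | 0.860 | 3.5 | 0.688 | 6.9 |

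Simulation agrees with the closed form to within about 0.002. In it, censoring at the last imaged time point was within 0.003 of the truth.

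**3. Scheduled visits only, with no late off-study visit.** A second simulation used the vaccine-naïve visit schedule with semi-annual boosts. Assumptions: recurrence medians of 9.9, 18 and 24 months, withdrawal of 5–30% per year, and a withdrawal hazard either unchanged or tripled after undetected recurrence. Last-visit minus last-scan censoring gave:

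- common scan grid: 0.0 points in every setting;
- scan dates varying by ±30 days: 0.14–2.0 points at 12 months and 0.25–2.45 at 24;
- the same, with half of recurrences found at unscheduled scans: 0.11–1.45 and 0.17–1.57.

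These are differences between two rules, not distances from the truth. When withdrawal was unrelated to recurrence, last-visit censoring was level with full follow-up on the same scans, or up to 1.6 points below it.

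**4. Withdrawal tied to undetected recurrence.** With an 18-month median and 20% withdrawal per year, 24-month PFS on a common grid was 50.6% under both rules, against 46.6% with full follow-up. With varying scan dates it was 49.9% (last visit), 48.5% (last scan) and 46.7% (full follow-up).

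**5. Scale.** With PFS near 50% and 40–45 patients, the standard error is about √(0.25/40) = 7.9 to √(0.25/45) = 7.5 points.

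**The case against.** The strongest case against is that follow-up visit in 4.3.1 means a recurrence evaluation. The same paragraph says that Johns Hopkins patients "will be followed every 3 months and evaluated for recurrence", its example visits are the pre-boost exams, which include CT, and it requires common evaluation points. That reading is possible, but it is nowhere stated.

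A reader might infer that every visit without a scan inflates PFS. The documents do not support this: the scheduled ones fall before the next scan and have no effect on a common grid.

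A reader might also infer that withdrawing patients routinely leave unscanned. Section 3.4.1 does list CT at the off-study visit. Section 3.4.6 sets its Day 28 tests beside 28 days of follow-up after the last vaccine, which most naturally puts that visit well before the next scan. A later date is not excluded, and the two sections conflict.

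Dating deaths back to the last visit pulls PFS the other way, and 4.3.1 already calls the results extremely preliminary, with no formal comparison. Both facts limit the consequence but do not settle the censoring date.

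**Conclusion.** The point holds in a limited form. The stated rule can credit recurrence-free time that nobody assessed, and PFS can then be biased upward, but only when a patient's last visit without imaging falls at or after a time point at which others' recurrences are read.

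The size rests on w. At month 8 the bias is under 1 point for w of 1–2% and about 2–9 points for w of 10–20%; both ranges are assumed. The larger figures need 10–20% of patients at each scan to leave in exactly this way, and nothing in the documents supports treating that as expected. If scan dates vary, scheduled visits alone move the estimate by about 0.1–2.5 points relative to last-scan censoring. That is small beside a standard error of 7–8 points.

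A flat statement that PFS is biased upward would go too far. So would a claim that last-scan censoring makes PFS unbiased: bias from withdrawal related to undetected recurrence largely remains. Severity is minor, since PFS is secondary and descriptive. It is a cheap improvement.

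**What to change.** Replace the withdrawal sentence in 4.3.1 with:

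> A patient who withdraws without diagnosed recurrence is censored at the last time point (common time point in the whole-cohort analysis, scan date in the Johns Hopkins analysis) at which CT or MRI showed no recurrence. Visits or contacts without imaging do not extend PFS.

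Reconcile the off-study list in 3.4.1, its provision for patients who cannot return, and 3.4.6, so that it is clear whether imaging belongs to the off-study assessment. A sensitivity analysis counting withdrawal without a scan as recurrence would show how far related withdrawal could matter.

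**Cost.** One sentence; scan dates are already collected. PFS becomes slightly less favourable. Where actual scan dates vary, censoring at the scan date can fall somewhat below full follow-up. In one simulated setting with unrelated withdrawal (18-month median, 20% per year), 24-month PFS was 44.7% with last-scan censoring, 45.8% with last-visit censoring and 46.8% with full follow-up. Using the common time point in the whole-cohort analysis avoids this.
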